## 8.3. Recording and Reporting SAEs and USADEs

All AEs, SAEs and device deficiencies must be recorded from the time of written informed consent until 26 weeks after the insertion date.

All AEs and device deficiencies occurring during the duration of the study must be reported by the investigator within the CRF. The PI is responsible for checking for AEs and SADEs when participants attend for treatment and follow-up.

The following events are considered reportable:

- Any SAE (whether initially considered device related or not)
- Any device deficiency that might have led to a SAE if:
  - o Suitable action had not been taken or
  - o Intervention had not been made or
  - If circumstances had been less fortunate.
- New findings/updates in relation to already reported events

All reportable events must be recorded by the investigator using the Sponsor's SAE reporting form and emailed to UHDB within 3 calendar days of the research team becoming aware of the event; even if not all information is available at the time (further information should be provided on the Sponsor's SAE Follow Up Report Form). Any change of condition or other follow-up information should be sent to the Sponsor as soon as it is available, or at least within 3 working days of the information becoming available. Events will be followed up until the event has been resolved or a final outcome has been reached. Safety information will be reviewed during trial management group meetings.

## **UHDB contact information**:

Email: [contact].

[contact] or [name] (must be followed up with a written report).

For each reportable event the following information will be collected:

- Full details of the event, including a diagnosis
- MedDRA coding (system organ class and preferred term)
- Duration (start and end dates)
- Seriousness criteria
- Outcome.
- Action taken.
- Causality (i.e. related to investigational medical device)
- Expectedness

Safety information will be reviewed for ongoing assessment of the risk/ benefit during study management group meetings as per the trial monitoring plan.

#### 8.3.1. Assessment of AEs and SAEs

#### 8.3.1.1 Severity

The investigator should determine the severity of the AE;

- Mild: no interference with daily activities.
- Moderate: moderate interference with daily activities.

• Severe: considerable interference with daily activities (e.g. inability to work).

**NOTE**: to avoid confusion or misunderstanding the term "severe" is used to describe the intensity of the event, which may be of relatively minor medical significance, and is NOT the same as "serious" which is described in the safety definitions.

## 8.3.1.2 Causality

Clinical judgement should be used to determine the relationship between use of the investigational medical device (including the medical-surgical procedure) and the occurrence of each AE;

- Not-related: relationship to the device or procedures can be excluded when:
  - The event is not a known side effect of the product category the device belongs to or of similar devices and procedures;
  - The event has no temporal relationship with the use of the investigational device or the procedures;
  - The serious event does not follow a known response pattern to the medical device (if the response pattern is previously known) and is biologically implausible;
  - The discontinuation of medical device application or the reduction of the level of activation/exposure when clinically feasible and reintroduction of its use (or increase of the level of activation/exposure), do not impact on the serious event;
  - The event involves a body-site or an organ not expected to be affected by the device or procedure;
  - The serious event can be attributed to another cause (e.g. an underlying or concurrent illness/ clinical condition, an effect of another device, drug, treatment or other risk factors);
  - The event does not depend on a false result given by the investigational device used for diagnosis, when applicable;
  - Harms to the subject are not clearly due to use error;
  - In order to establish the non-relatedness, not all the criteria listed above might be met at the same time, depending on the type of device/procedures and the serious event.
- Unlikely: the relationship with the use of the device seems not relevant and/or the event can be reasonably explained by another cause, but additional information may be obtained.
- Possible: the relationship with the use of the investigational device is weak but cannot be ruled out completely. Alternative causes are also possible (e.g. an underlying or concurrent illness/ clinical condition or/and an effect of another device, drug or treatment). Cases were relatedness cannot be assessed or no information has been obtained should also be classified as possible.
- Probable: the relationship with the use of the investigational device seems relevant and/or the event cannot reasonably explained by another cause, but additional information may be obtained.
- Causal relationship: the serious event is associated with the investigational device or with procedures beyond reasonable doubt when:
  - The event is a known side effect of the product category the device belongs to or of similar devices and procedures;
  - The event has a temporal relationship with investigational device use/application or

procedures;

- The event involves a body-site or organ that
  - The investigational device or procedures are applied to;
  - The investigational device or procedures have an effect on;
- The serious event follows a known response pattern to the medical device (if the response pattern is previously known);
- The discontinuation of medical device application (or reduction of the level of activation/exposure) and reintroduction of its use (or increase of the level of activation/exposure), impact on the serious event (when clinically feasible);
- Other possible causes (e.g. an underlying or concurrent illness/ clinical condition or/and an effect of another device, drug or treatment) have been adequately ruled out;
- Harm to the subject is due to error in use;
- The event depends on a false result given by the investigational device used for diagnosis, when applicable;
- In order to establish the relatedness, not all the criteria listed above might be met at the same time, depending on the type of device/procedures and the serious event.

Assessment of causality must be made by a medically qualified doctor (usually the principal investigator). If a doctor is unavailable, initial reports should be submitted to UHDB without the causality assessment but they must be followed up with a medical assessment as soon as possible.

## 8.3.1.3 Expectedness

The assessment of expectedness is only required if the event is deemed to be related to use of the investigational medical device as per the clinical investigation plan.

- Expected: Reaction previously identified and described in the investigator brochure/ clinical investigation plan.
- Unexpected: Reaction not previously described in the investigator brochure/ clinical investigation plan.

The expectedness assessment is delegated to the CI.

#### 8.3.2. Expedited reporting

For trials of investigational medical devices that are non CE-marked or CE marked but being used outside of their intended use(s) covered by the CI mark all reportable events must be reported to the MHRA ([contact]) using the MEDDEV 2.7/3 SAE reporting table and the manufacturer. In addition all USADEs must be reported to the REC.

## 8.4. Pregnancy reporting

If a participant, or the partner of a participant, becomes pregnant or is suspected to be pregnant from the time of consent up to 6 months following the fitting of the investigational medical device the

investigator must notify the Sponsor within 14 days of becoming aware of the pregnancy using the Sponsor's pregnancy notification form. All pregnancies will be followed up until the outcome of the pregnancy; if at any stage an event occurs that meets the criterion for an SAE then it must be reported as such.

## 8.5. Reporting Urgent Safety Measures

If any urgent safety measure is taken the research team should inform the Sponsor with 24 hours using the Sponsors safety incident reporting form. The Sponsor will inform the REC and participating sites of the measures taken and the circumstances giving rise to those measures within 3 days on implementation of the urgent safety measure.

## 9. DATA HANDLING

## 9.1. System and Compliance

All data will be collected on a paper CRF for each participant where each participant will be assigned a unique trial ID. Each participant will be assigned a trial identity code number, for use on CRFs, other trial documents and the electronic database. The key linking participant identifiable data to the trial ID will be stored in a password protected file on a secure server (University Hospitals of Derby and Burton NHS Foundation Trust). The electronic results system will be the source document for haematological, biochemical and microbiology laboratory test results.

Only study staff shall have access to study documentation other than the regulatory requirements listed below. The investigators will keep records of all participating patients, all original signed informed consent forms and copies of the CRF pages in the Investigator Site File. Data will be added into the CRF directly and therefore it will act as a source document.

Patent reported outcome measures will be recorded on paper and filed in the CRF on Completion Any data used for dissemination purposes will be anonymised, ensuring participants cannot be identified from data.

#### 9.2. Source Data

See section 10.1

#### 9.3. Data Workflow

The CRF will be managed by the investigatory team and data from the CRF will be entered into an electronic database (excel) by trial ID which will be held securely and password protected. All data will be stored on a secure web server (University Hospitals of Derby and Burton NHS Foundation Trust). Access will be restricted by user identifiers and passwords (encrypted using a one way encryption

method). Information about the study in the participant's medical records / hospital notes will be treated confidentially in the same way as all other confidential medical information. Electronic data will be backed up every 24 hours to both local and remote media in encrypted format as per the standard server backup process.

## 9.4. Data Access and Security

Only the chief investigator and co-investigators will have access to the anonymised data. Direct access will be granted to authorised representatives from the Sponsor, host institution and the regulatory authorities to permit study-related monitoring, audits and inspections.

## 9.5. Archiving

At the end of the trial, following completion of the end of trial report, UHDB will securely archive all centrally held trial related documentation for a minimum of 5 years. At the end of the defined archive period arrangements for confidential destruction will be made. It is the responsibility of each PI to ensure that data and all essential documents relating to the trial are retained securely for a minimum of 5 years after the end of trial, and in accordance with national legislation.

UHDB will notify sites when trial documentation held at sites may be archived, and then destroyed. All archived documents must continue to be available for inspection by appropriate authorities upon request.

## 10. STATISTICS AND DATA ANALYSIS

## 10.1. Sample Size Calculation

This is a feasibility study and a sample size calculation is therefore not required. The sample size is based on the number of PD catheters anticipated to be inserted during the recruitment period. Observation of 40 participants for 6 months with yield a total observation period of 240 patient months which should provide adequate data for comparison with nationally reported PD peritonitis rates and international quality standards (International Society of Peritoneal Dialysis recommends the rate should be below 0.4 episodes per patient year).

## 10.2. Planned Recruitment Rate

We aim to recruit 40 participants in 18 months. Based on data from the past 3 years, our clinical team places approximately 50 PD catheters per year. We therefore expect 75 catheters to be placed during the recruitment period of 18 months and will require a recruitment rate of 40/75 (53%). Based on our discussions with PPI representatives we believe that this is achievable.

## 10.3. Statistical Analysis

Statistical analysis will be performed by [name].

## **10.3.1.** Summary of Demographic/Baseline Data and Flow of Patients

Descriptive statistics will be presented to summarize the distribution of baseline variables. Baseline variables will include comprehensive demographic and clinical variables. The continuous baseline variables will be reported with means and 95% confidence intervals (95% CI), if shown to be normally distributed, using a normality plot, otherwise will be reported with medians and interquartile ranges (IQR). The categorical variables will be reported with frequencies and percentages.

## **10.3.2.** Primary Outcome Analysis

The primary outcome is adverse events. We will report the total number of each category of adverse event as well as the adverse event rate per participant observation month.

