## 2.1. Primary Objectives

For this feasibility study we will assess the safety and tolerability of the antimicrobial PD catheter, defined as the rate of adverse events attributable to the antimicrobials or the impregnation process encountered by PD patients.

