## 2.3. Primary Endpoint/ Outcome

The rate of adverse events attributable to the antimicrobials or the impregnation process encountered by PD patients.

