## 8. PHARMACOVIGILANCE

## 8.1. Definitions

Term	Definition
Adverse Event (AE) Adverse Device	Any untoward medical occurrence, unintended disease or injury, or untoward clinical signs (including abnormal laboratory findings) in subjects, users or other persons, where or not related to the investigational medical device and whether anticipated or unanticipated.
Effect (ADE)	
 
An adverse event related to the use of an investigational medical device.
 
NOTE: this definition includes: 
 
AEs resulting from insufficient or inadequate instructions for use, deployment, implantation, installation, or operation, or any malfunction of the investigational medical device.
 
Any event resulting from use error or from intentional misuse of the
 

	
 
investigational medical device.
 
'Comparator' if the comparator is a medical device.
 

Serious Adverse Event (SAE)	
 
An adverse event that led to any of the following: 
 
death
 
serious deterioration in the health of the subject, users, or other persons as defined by one of more of the following 
 
a life-threatening illness or injury, or
 
a permanent impairment of a body structure or a body function including chronic diseases, or
 
in-patient of prolonged hospitalisation, or
 
medical or surgical intervention to prevent life-threatening illness or injury, or permanent impairment to a body structure of a body function,
 
 
 
foetal distress, foetal death, a congenital abnormality, or birth defect including physical or mental impairment.
 
 NOTE: Planned hospitalisation for a pre-existing condition, or a procedure required by the CIP without a serious deterioration in health, is not considered a SAE.

Serious Adverse	An adverse device effect that has resulted in any of the consequences
Device Effect (SADE)	characteristic of a serious adverse event.
Unanticipated Serious Adverse Device Effect (USADE)	A serious adverse device effect which by its nature, incidence, severity or outcome has not been identified in the current risk assessment. NOTE: Anticipated serious adverse device effect (ASADE) is an effect which by
	its nature, incidence, severity or outcome has been identified in the risk assessment.

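### The primary endpoint is adverse events attributable to the antimicrobials or impregnation, but section 10.3.2 analyses all adverse events and the protocol states no rule for identifying the attributable ones

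*Protocol*

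**What the plan says.** Protocol section 2.1 sets safety and tolerability as the primary objective, "defined as the rate of adverse events attributable to the antimicrobials or the impregnation process encountered by PD patients". Section 2.3 repeats this as the primary endpoint: "The rate of adverse events attributable to the antimicrobials or the impregnation process encountered by PD patients".

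Section 10.3.2 describes what will be analysed: "The primary outcome is adverse events. We will report the total number of each category of adverse event". A second measure is then added over follow-up time, worded "as well as the adverse event rate per participant observation month". Neither measure has an attribution condition, and the Trial Summary likewise lists only adverse events as the primary outcome measure. Under section 8.1 an AE counts whether or not "related to the investigational medical device and whether anticipated or unanticipated". The narrower adverse device effect is "An adverse event related to the use of an investigational medical device", which again concerns the whole device.

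Section 8.3.1.2 asks the doctor to judge the "relationship between use of the investigational medical device (including the medical-surgical procedure) and the occurrence of each AE". For reportable events, section 8.3 lists one causality item, also about the device. Section 7.1 (risk assessment summary) separates the accepted risks of every PD catheter from the additional risks of impregnation, and states that there is no comparator device.

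**The concern.** The definition and the analysis of the primary endpoint use different numerators. One counts events caused by the drugs or the impregnation. The other counts every untoward event in patients with end-stage kidney disease who are having a catheter inserted and starting dialysis.

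The study asks whether the impregnated catheter is well tolerated and whether the data support efficacy studies and commercial adoption (section 2). In a single-arm study, an all-cause rate mixes the new risk with the risks of any PD catheter, of insertion and of the underlying disease. A reader given that rate as the primary result could not tell how much of it concerns the impregnation. If attribution is not recorded while the evidence is fresh, it has to be reconstructed afterwards.

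**Working it through.** **Numerators side by side**

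| Source | What is counted |
|---|---|
| 2.1, 2.3 | AEs attributable to the antimicrobials or impregnation |
| Trial Summary, 10.3.2 | AEs, no restriction |
| 8.1, adverse device effect | AEs related to use of the device, including use error |
| 8.3.1.2 | Relatedness to the device including the procedure, five levels |

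No row below the first identifies the events in the first. One criterion for the top causality level reads "The event is a known side effect of the product category the device belongs to or of similar devices and procedures". A catheter migration, which any PD catheter can undergo, could therefore be rated causal without any involvement of the antimicrobials.

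The time windows differ too. AEs are recorded from consent (8.3), and insertion is normally offered within 1 to 3 weeks (6.1.1). Events before insertion can enter the count in 10.3.2 although no catheter was in place.

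**Size of the difference (illustration)**

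Inputs: 40 participants and 6 months each (10.1); local peritonitis rate 0.37 per patient-year (8.2); national rate 40 to 50 episodes per 100 patient-years (Background).

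1. The plan's own figure: 40 × 6 = 240 participant-months, as stated in 10.1. 240 / 12 = 20 patient-years.
2. Expected peritonitis if the impregnation has no effect: 0.37 × 20 = 7.4 episodes, or 7.4 / 240 = 0.031 per participant-month. At the national rates: 0.40 × 20 = 8 and 0.50 × 20 = 10 episodes.
3. The endpoint as defined, if no event is attributable: 0 / 240 = 0. The exact two-sided 95% Poisson upper limit is −ln(0.025) / 240 = 3.689 / 240 = 0.0154 per participant-month.

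Steps 2 and 3 assume full follow-up. Participants leave the study if the catheter is removed (6.5), so at 0.37 per year 7.4 is a ceiling and 0.0154 is the tightest limit available. If exposure were, say, 200 months (an assumption), the figures would be 0.37 × 200 / 12 = 6.2 episodes and 3.689 / 200 = 0.0184 per month.

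Step 2 also assumes that peritonitis is counted as an AE. Section 8.3 requires all AEs in the CRF. Section 8.2 exempts foreseeable events from reporting to the sponsor and mentions only the medical records for them.

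**The case against.** **The statistical analysis plan may settle it.** It is not shown and could define the numerator. But 10.3.2 states a different outcome from 2.3, which is a contradiction rather than a detail left for later. A later plan can filter only on what was collected or can be adjudicated.

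**The categories may be AE, adverse device effect, SAE and so on.** That reading is open, because the term is undefined. Device-related counts would then be reported, so it is too strong to say that only all-cause totals will appear. Those counts would still be for the whole device, and the stated rate would still be for all AEs.

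**A reader might infer that the endpoint cannot be computed.** The documents do not support that. All AEs go into the CRF, a doctor assesses causality, and reportable events carry a diagnosis, coding and details. Section 8.2 also singles out suspected reactions to the catheter and infections resistant to its antibiotics. Attribution could be adjudicated from such records, and the CRF itself is not shown. What is absent is a stated field or rule.

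**A reader might also infer that attribution is the only way to isolate the new risk.** That is wrong for infection. The protocol plans comparison with local and national rates, and 10.3.3 reports peritonitis, exit-site/tunnel infection and technique failure separately. Peritonitis can therefore be picked out of the AE total. For other harms no external comparison is described.

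**It is a descriptive feasibility study with no AE threshold.** This stands. Nothing in the plan turns a high all-cause rate into a failed study, so the point rests on the mismatch in definition and not on the illustrative counts.

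**Conclusion.** The point holds. The primary endpoint as defined and the primary analysis as written are different quantities, and nothing stated in the protocol leads from one to the other. This should be corrected before the data are analysed, because it concerns the primary outcome.

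As an indication of size, the reported rate could carry about 0.031 per month from background peritonitis alone, while the defined endpoint could be 0 with an upper limit of 0.0154 per month. These figures assume 240 participant-months, a constant rate of 0.37 per patient-year, Poisson counts and peritonitis being counted as an AE. The documents assume no attributable rate, so they give no corrected figure to set against these.

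The stronger conclusions, that the endpoint is beyond recovery or that the catheter would be judged unsafe, do not follow.

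**What to change.** 1. For each AE, record prospectively a medical assessment of relatedness to the antimicrobials or the impregnation, distinct from the base catheter and the insertion procedure. The existing five-level scale can be used.
2. In 10.3.2, make the primary analysis the rate of AEs so attributed per participant-month from catheter insertion, with an exact 95% confidence interval and a stated cut-off on the scale.
3. Section 8.3.1.2 places cases whose relatedness cannot be assessed in the possible level. A cut-off at possible or above would therefore bring them into the primary numerator. Report them separately, or show the rate with and without them.
4. Report all-cause and any-device-related AEs as supporting summaries, and say what the categories in 10.3.2 are.
5. Align the Trial Summary with section 2.3.

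The cost is a little extra rating work by a doctor for each AE, a change to the CRF, and a protocol amendment under section 12.9. No visits or participants are added.
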